3 THE TRIAL

3.1 Trial design

This is a non-Inferior, Multi-Center, Prospective Randomized Controlled Trial ((1:1 randomization) conducted in China. The study aims to consecutively enroll up to 724 procedures over the course of one year at 10 EP centers with non-fluoroscopic labs accredited by the Chinese Heart Rhythm Society. The anticipated total study duration is 36 months, with a follow-up period of 12 months for each participant. The study will be completed after the last enrolled subject has finished the 12-month follow-up period.

Following informed consent, obtained either during the pre-procedure office visit or during hospitalization for the procedure, baseline data will be collected. This data will include patient demographics, medical history, prior treatments, and laboratory test results.

The initial enrollment ratio between PFA and RF was projected to be evenly distributed at 50% each. Peri-procedural data, including procedural details, ablation strategies, acute success rates, VISITAG parameters, and any complications or adverse events, will be recorded up to the patient's discharge.

Post-discharge, participants will undergo follow-up evaluations at 1,2, 3,6,9,12 months after the procedure. The follow-up schedule will remain unchanged even if a repeat ablation procedure is required.

3.2 Study Rationale and Objective

This randomized controlled trial aims to evaluate the **efficacy, peri-procedural safety, and clinical outcomes** of catheter ablation performed in non-fluoroscopic EP labs compared to procedures in conventional DSA lab.

With the rapid adoption of non-fluoroscopic EP labs in China, it is essential to assess their performance to ensure safe and effective care. We hypothesize that non-fluoroscopic procedures will demonstrate non-inferior safety and efficacy to fluoroscopy-guided ablations, while offering benefits such as reduced costs, minimized radiation exposure for physicians, and improved environmental sustainability.

This study will provide evidence to guide clinical practice, improve patient care, and support the broader adoption of non-fluoroscopic EP technologies, enhancing access to advanced arrhythmia treatments and optimizing outcomes for patients with AF.

3.3 Inclusion/exclusion criteria

Inclusion criteria

Subjects must meet all the following inclusion criteria to be eligible for participation in this trial.

- 1) Age: ≥ 18 years
- 2) Patients diagnosed with paroxysmal AF or persistent AF with a duration of 1 year or less, who are referred for catheter ablation.
- 3) Patients referred for catheter ablation as a first-time intervention (no prior catheter ablation or surgical procedures for AF).
- 4) The patient is able and willing to provide written informed consent

Exclusion criteria

Subjects who meet any of the following exclusion criteria are not eligible for enrollment.

- 1) Patients with contraindication to anticoagulation
- 2) Patients with contraindication to right or left sided cardiac catheterization
- 3) Patients scheduled for AF ablation procedures other than PVI and requiring X-ray fluoroscopy, such as VOM ablation, epicardial ablation, LAAO, CAG, etc
- 4) Serious known concomitant disease with a life expectancy of < 1 year
- 5) MI, CABG, or PCI within the preceding 3 months
- 6) Left atrial diameter > 55 mm
- 7) LVEF $< 30\%$
- 8) NYHA class III or IV
- 9) Awaiting cardiac transplantation or other cardiac surgery within 12 months.
- 10) History of a documented thromboembolic event within the past 6 weeks.
- 11) Heart or vascular malformation that impedes catheter access or vascular puncture.
- 12) Current enrollment in an investigational study evaluating another device or drug.
- 13) Acute illness, active systemic infection, or sepsis.
- 14) Significant congenital anomaly or a medical problem that in the opinion of the investigator would preclude enrollment in this trial.

3.4 Study Endpoints

3.4.1 Primary endpoints

The primary efficacy endpoint is freedom from any documented atrial arrhythmia, including AF, atrial tachycardia or atrial flutter episodes lasting longer than 30 seconds without antiarrhythmic drugs, for 12 months after the index ablation procedure, excluding a 3-month blanking period. The continuation or reinitiation of class I or class III antiarrhythmic drugs after the 3-month post ablation blanking period, as well as electric cardioversion or catheter ablation for any atrial arrhythmias, are considered treatment failures for the primary end point.

The primary safety endpoint is a composite of the following prespecified procedure-related serious adverse events:

- Major vascular complication or major bleeding within the first 7 days post procedure.
- Development of a clinically significant pericardial effusion.
- Transient ischemic attack.
- Stroke.
- Myocardial infarction.
- Severe pulmonary vein stenosis.
- Atrial-esophageal fistula, or phrenic nerve injury within 3 months.
- Death.

3.4.2 Secondary endpoints

[figure not shown]
- The acute success of the procedure.
- The proportion of intraoperative conversion to using X-ray.
- Utilization of lead personal protective equipment (PPE) and wear time.Well-being survey of staff.
- The proportion of patients with recurrence of targeted arrhythmia during the first 90 days post-ablation.
- Early recurrence of atrial arrhythmias, defined as any AF/AFL/AT episode lasting >30 seconds occurring during the blanking period.
- Late recurrence of atrial arrhythmias, defined as any documented AF/AFL/AT episode lasting >30 seconds occurring after the blanking period and up to 12 months.
- Impact of early recurrence on late recurrence, assessed through survival analysis and multivariable adjustment to evaluate whether early recurrence predicts subsequent late recurrence.
- AF burden, assessed by scheduled rhythm monitoring (e.g., 7-day Holter at 3, 6, 9, and 12 months), expressed as the proportion of time spent in AF during the monitoring period.
- Incidence of peri-procedural complication.
- Total procedure duration, ablation time.
- changes in quality-of-life (using the AF Effect on Quality of Life (AFQT) and the EuroQol Health-Related Quality-of-Life 3-Level (EQ-5D-3L)).

3.5 Sample Size

For **efficacy** as the primary endpoint, sample-size was calculated by non-inferiority log-rank test with 1:1 design. The expected recurrence rate of AF is 30% for control group based on previous studies and our experience, and a hazard ratio of 1.3 was used for establish non-inferiority. Based on a power of 80% and an alpha of 0.05, proportion lost to follow up 5%, a sample size of **724 patients (362 for each group)** was estimated.

Safety endpoints will still be collected in detail and analyzed for comparison between the groups, but they will not be used to determine the sample size.

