Exclusion Criteria	
Subjects who meet any of the following exclusion criteria are not eligible for enrollment.
 
 • Patients with contraindication to anticoagulation or to right or left sided cardiac catheterization • Patients scheduled for AF ablation procedures other than PVI and requiring X-ray fluoroscopy, such as VOM ablation, epicardial ablation, LAAO, CAG, etc. • Serious known concomitant disease with a life expectancy of < 1 year • MI, CABG, or PCI within the preceding 3 months • Left atrial diameter >55 mm • LVEF<30% • NYHA class III or IV • Awaiting cardiac transplantation or other cardiac surgery within 12 months. • History of a documented thromboembolic event within the past 6 weeks. • Heart or vascular malformation that impedes catheter access or vascular puncture. • Current enrollment in an investigational study evaluating another device or drug. • Acute illness, active systemic infection, or sepsis. • Significant congenital anomaly or a medical problem that in the opinion of the investigator would preclude enrollment in this trial.
Type	A Non-Inferior, Multi-Center, Prospective Randomized Controlled Trial
Design	Sample Size Justification

1) The sample size calculation will be based on the primary efficacy endpoint.

Sample-size was calculated by non-inferiority log-rank test with 1:1 design. The expected recurrence rate of AF is 30% for control group based on previous studies and our experience, and a hazard ratio of 1.3 was used for establish non-inferiority. Based on a power of 80% and an alpha of 0.05, proportion lost to follow up 5%, **a sample size of 724 patients** (362 for each group) was estimated.

Non-Inferiority Logrank Tests

Numeric Results in Terms of Sample Size

[figure not shown]
Power	N1	N2	N	Equiv			Actual			Ref			Acc-			Ref	Trt	to	Trt	to	Ref	Alp
				Haz	Haz	Haz	Ref	Acc-	Time/	Total	Ref	Trt	Ref	Trt	Trt							
				Ratio	Ratio	Rate	Pat'n	Time	Total	Ref	Trt	Ref	Trt	Trt	Ref	0.0500	0.0500	0.0000	0.0000	0.05		
0.8003	361	362	723	1.30	1.00	0.3000	Equal	1 / 3	0.0500	0.0500	0.0000	0.0000	0.0000	0.0000	0.05							

References

Jung, Sin-Ho; Kang, Sun J.; McCall, Linda M.; Blumenstein, Brent. 2005. 'Sample Sizes Computation for Two-Sample Noninferiority Log-Rank Test', *J. of Biopharmaceutical Statistics*, Volume 15, pages 969-979. Lakatos, Edward. 1988. 'Sample Sizes Based on the Log-Rank Statistic in Complex Clinical Trials', *Biometrika* Volume 44, March, pages 229-241.

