7.5.4 SUSARs Reporting

Suspected Unexpected Serious Adverse Reactions [SUSARs] will undergo expedited reporting to relevant regulatory authorities (e.g., research ethics committees, National Medical Products Administration, and National Health

Commission of the People's Republic of China). Investigators must report all SUSARs to sponsor as soon as possible and 24h of learning of the event. These SUSARs will be centrally reviewed and reported by the sponsor as soon as possible:

For fatal or life-threatening SUSARs, sponsor must report as soon as possible and within 7 days of learning of the events. Active follow-up must be completed within the following 8 days (The first day of learning of the event is considered 0 day).

For fatal or life-threatening SUSARs, sponsor must report as soon as possible and within 15 days of learning of the events.

8. Statistical analysis

Continuous variables are expressed as mean \pm SD if normally distributed or median (interquartile range [IQR]) if not normally distributed. Intergroup differences will be compared by student's t-test (normally distributed data with equal variance) or Mann-Whitney U test (failed either normality or equal variance test). Categorical variables will be presented as percentages and compared by using the Chi-square test or Fisher's exact test. The Kaplan-Meier method will be used to describe event-free rates over time. The statistical significance for all tests will be accepted at $P < 0.05$.

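### The 80% power claimed for 724 patients assumes 2 to 3 years at risk per patient; with the protocol's 12-month follow-up and 30% recurrence, power is about 60%

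*Protocol*

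**What the plan says.** Section 3.5 of the protocol, and the same text in the synopsis, set out the calculation. The method is "sample-size was calculated by non-inferiority log-rank test with 1:1 design". The event-rate assumption is "The expected recurrence rate of AF is 30% for control group based on previous studies and our experience", with no time unit. The margin is "a hazard ratio of 1.3 was used for establish non-inferiority". The remaining inputs are "Based on a power of 80% and an alpha of 0.05, proportion lost to follow up 5" (per cent). The result is 724 patients, 362 per group.

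The synopsis also prints the software row: power 0.8003, N = 723, equivalence hazard ratio 1.30, actual hazard ratio 1.00, reference hazard rate 0.3000, accrual/total time 1 / 3, losses 0.0500 and alpha 0.05.

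On follow-up, Section 3.1 says: "The anticipated total study duration is 36 months, with a follow-up period of 12 months for each participant". Enrolment is planned over one year. Section 3.4.1 defines the primary efficacy endpoint over 12 months, "excluding a 3-month blanking period". Table 1 has no visit after month 12, and the synopsis ends the study when the last patient completes 12 months.

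Section 8 sets the general significance rule, "The statistical significance for all tests will be accepted at" P < 0.05, without saying one- or two-sided.

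**The concern.** The power of a log-rank non-inferiority test depends on the number of events, and so on how long patients are at risk. An accrual time of 1 and a total time of 3 mean that the first patient is observed for 3 years and the last for 2. No patient in this trial is followed beyond 12 months for the primary endpoint. The 36-month calendar duration appears to have been entered as the total time, and the 30% recurrence as a yearly hazard rather than as a 12-month proportion.

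The primary efficacy endpoint is the only basis for the sample size, since the protocol excludes safety from the sizing. If the event count is overstated, the trial may well end inconclusive even when the two labs perform equally. Low power does not raise the type I error, so a positive non-inferiority result would still be valid. What is at stake is the chance of reaching one, and a power figure that is wrong as stated.

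**Working it through.** **Inputs.** From Section 3.5 and the synopsis output: margin HR 1.3, true HR 1.0, 1:1 allocation, alpha 0.05, power 80%, loss 5%, hazard 0.3000, accrual/total 1 / 3. From Sections 3.1 and 3.4.1: 12 months of follow-up and a 12-month endpoint. The output prints no time unit; years is an inference, tested in step 2.

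**1. Events needed.** With one-sided 0.05 and 80% power:

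D = 4 × (1.645 + 0.842)² / (ln 1.3)² ≈ 359.3, so 360 events.

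**2. Reproducing the printed power.** Take hazard h = 0.30 per year, loss hazard l = −ln(0.95) = 0.0513 per year, uniform accrual over A = 1 year and total time T = 3 years. With t = h + l = 0.3513:

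p = (h/t) × [1 − (e^(−t(T−A)) − e^(−tT)) / (tA)] = 0.4973

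- Events: 723 × 0.4973 = 359.6.
- Power = Φ(√359.6 / 2 × ln 1.3 − 1.645) = 0.8003, the printed value to four decimals.

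Without loss, the same inputs imply that about 53% of patients recur. The alternatives tried do not give 723:

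| Change to the inputs | N for 80% power |
|---|---|
| two-sided 0.05 | about 918 |
| no loss | 685 |
| 30% converted to hazard 0.357 per year, still over 3 years | about 646 |

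**3. The design as written: 724 patients, 12 months.** Power = Φ(√D / 2 × ln 1.3 − 1.645).

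| Reading of the 30% | Events D | Power, one-sided 0.05 |
|---|---|---|
| 30% failing by 12 months, no loss: 724 × 0.30 | 217 | 61.4% |
| 30% by 12 months (hazard 0.357), exponential 5% loss | 212 | 60.5% |
| 30% by 12 months, 5% removed: 724 × 0.30 × 0.95 | 206 | 59.5% |
| hazard 0.30 per year over 12 months | 183–188 | 55–56% |
| hazard 0.30 per year over the 9 months after blanking | 143–146 | 47–48% |

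For the third row: √206.3 / 2 × 0.2624 = 1.884, and Φ(1.884 − 1.645) = Φ(0.239) = 0.595.

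**4. Simulation.** With 4,000 runs of the non-inferiority log-rank test, the software inputs gave 79.6% power (360 events). Twelve months with 30% failure and 5% loss gave 60.8% (212 events).

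**5. What would give 80%.**

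- Failure rate: 359.3 / 724 = 49.6% without loss, or 52.2% after dividing by 0.95. The protocol expects 30%.
- Sample size at 30% over 12 months: 360 / 0.30 = 1,200 without loss, about 1,229 with exponential loss, and 360 / 0.30 / 0.95 = 1,264 with simple inflation.
- Margin with 80% power at 206 to 217 events: exp(2 × 2.487 / √D) = 1.41 to 1.40.

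**The case against.** **The 30% is described as AF recurrence, while the primary endpoint is wider.** It also counts flutter, tachycardia, class I or III drug use after blanking, cardioversion and repeat ablation. Composite failure could therefore exceed 30%. This stands as a caution on the exact figure. It does not rescue the 80%: failure of 35% gives 65 to 67% power and 40% gives 70 to 72% (illustrative rates, not in the protocol).

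**The output table is damaged and shows no time unit.** True, but the four-decimal match in step 2 leaves little doubt about what was entered. That the 36-month duration was the source of the 3 remains an inference.

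**Section 1.2.2 speaks of success after a year or longer.** That is a loosely worded research question. The endpoint definition, the visit schedule and the completion rule all stop at 12 months. Even if patients were followed to a common close-out 2 years after study start, which is one year of accrual plus one, power would be only 67 to 72%.

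**A non-inferiority test is one-sided by nature, and the details may be in a SAP.** Largely accepted. Sidedness is a clarification here, and the shortfall above is computed at the more favourable one-sided 0.05. It still matters to state it, because 724 depends on it: at one-sided 0.025, 30% recurrence would give 47 to 49%.

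**Conclusion.** The concern holds. The software arithmetic is right for its inputs, but the inputs describe a different trial. With the protocol's 12-month follow-up, 724 patients yield about 206 to 217 events against the 360 needed, and power is 59 to 61% rather than 80%.

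This rests on three assumptions: 30% is the cumulative 12-month failure on the primary endpoint, the true hazard ratio is 1.0, and alpha is one-sided 0.05. Reading 30% as a yearly hazard lowers power to between 47 and 56%. Composite failure of 35 to 40% would raise it to between 65 and 72%. Reaching 80% would need about half of all patients to fail within 12 months, which contradicts the protocol's own expectation. The stated power must be corrected.

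**What to change.** Rerun the calculation with at most one year at risk per patient and 30% cumulative failure at 12 months on the primary endpoint as defined in Section 3.4.1. In the synopsis and Section 3.5:

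- Give the time horizon of the 30% and say that it refers to the composite endpoint.
- Replace the 80% with the power that 724 delivers, about 60% on these inputs.
- State the expected number of events, about 206 to 217.
- State that alpha 0.05 is one-sided.
- Remove or replace the output row with accrual/total time 1 / 3.

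This costs one software rerun and the rewording of two paragraphs. It needs no extra patients, but the stated power becomes less favourable.

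If the sponsor wants to restore 80%, about 1,200 to 1,264 patients would be needed with 12-month follow-up. Following everyone to a common close-out would also add events: 67 to 72% power at 2 years, and 80 to 84% at 3 years with one-year accrual. That would replace the 12-month endpoint and extend the visit schedule, so it is a design change, not a correction.

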3.6 Study flowchart

3.7 Planned trial interventions

Ablation Procedure details (study and control group)

The study will target AF catheter ablation procedures. After obtaining written informed consent, eligible patients will be randomized in a 1:1 fashion to one of the following two groups:

Group 1: Non-Fluoroscopic Lab Group

1. Ablation procedures will utilize ICE and 3D mapping systems for non-fluoroscopic guidement. ICE is mandatory for real-time anatomical visualization.
2. No routine fluoroscopy will be used, except if deemed necessary for safety (e.g., complications or unexpected procedural difficulties), adhering to the ALARA principle.
3. Pulmonary vein isolation (PVI) will be the sole ablation strategy, following the study protocol.

Group 2: Fluoroscopic Lab Group (DSA Lab)

1. Ablation procedures will be conducted in a fluoroscopic lab. The use of ICE, 3D EP mapping systems, and other tools will follow the same recommendations as in the non-fluoroscopic lab group.
2. Radiation exposure will be closely monitored and minimized in accordance with the ALARA (As Low As Reasonably Achievable) principles when necessary.
3. Similar to Group 1, PVI will be the sole ablation strategy, as per protocol.

Ablation strategy

The primary ablation strategy for both groups will be **pulmonary vein isolation (PVI)**. Additional ablation, including but not limited to linear ablation, complex fractionated atrial electrogram (CFAE) ablation, or superior vena cava (SVC) isolation will not be allowed unless required in the presence of one the following:

- Documented atrial flutter (AFL) or atrial tachycardia (AT) observed during the procedure, or
- Arrhythmias originating from the specific region requiring intervention.

Energy Selection Principles

At the time of enrollment, the investigator will determine the planned ablation energy modality (radiofrequency [RF] or pulsed field [PF]) according to routine clinical practice, patient characteristics, procedural indications, device availability, and patient preference. The choice of energy modality is made prior to randomization, and the study protocol does not mandate or interfere with individual clinical decision-making.

Given the increasing adoption and availability of pulsed field ablation (PFA) in current clinical practice, and in order to maintain the external validity of the study in the future era when PFA is expected to become the predominant ablation modality, the study adopts a population-level expectation for patients enrolled after the effective date of this protocol version:

Without influencing individual clinical judgment, the cumulative proportion of PFA among subsequently enrolled patients is expected to progressively increase, with a target of achieving $\geq 50\text{-}60\%$ of all newly enrolled cases.

This expectation aims to optimize the overall energy composition of the study cohort to better reflect evolving clinical practice trends. It does not impose restrictions on individual patient-level energy selection and does not apply to participants enrolled prior to the implementation of this protocol amendment.

Recommendations

- 1) The configuration of the Non-fluoroscopic Lab needs to be in accordance with the latest expert consensus recommendations (Jiang C, et al. Pacing Clin Electrophysiol. 2023 Sep;46(9):1035-1048).

- 2) The use of ICE catheter is required for both groups. The application of ICE technology includes but is not limited to: visualizing the cardiac anatomy; guiding catheter placement, transeptal puncture (if necessary); constructing the geometry; monitoring intracardiac thrombus and cardiac effusion throughout the procedure.
- 3) Magnetic mapping catheters (e.g. Lasso, PentaRay, or DECANAV) is recommended to create the cardiac geometry.
- 4) A safe, rapid, and smooth plan for transfer to the DSA lab should be established if no mobile DSA equipment is available in the Non-fluoroscopic EP Lab. In the event of an emergency requiring the use of DSA, patient transfer should be completed in a minimum period to maximize patient safety.
- 5) If deemed necessary, X-ray imaging may be utilized to guide catheter placement and monitor for potential complications. The use of X-ray must adhere to the As Low As Reasonably Achievable (ALARA) principle, ensuring radiation exposure is minimized while maintaining procedural safety and effectiveness.

3.8 Clinical Equipoise

3.8.1 Sample Size Justification

Since complication rates are very low (estimated at 2-3% in the ICE group, based on literature²⁹⁻³² and our prior experience), conducting a controlled study focusing on safety endpoints is not feasible. Additionally, our previous registry study has already provided supporting evidence on safety. In this study, while safety endpoints will still be collected in detail and compared between the two groups, they will not be used to calculate the sample size. Instead, the sample size calculation will be based on the primary efficacy endpoint.

3.8.2 Ablation strategy

PVI is well-established as the cornerstone strategy for AF ablation, particularly for paroxysmal AF, its effectiveness in persistent AF remains a subject of ongoing investigation. There is currently no robust clinical evidence to support that additional ablation strategies provide superior outcomes for all persistent AF patients³³. Enhanced isolation of the vein of Marshall (EIVOM) has shown promise in improving outcomes for selected cases of persistent AF, particularly in addressing specific arrhythmogenic substrates. However, EIVOM is not universally applicable, as it often necessitates X-ray imaging and specialized techniques, which limit its use in fluoroscopy-free settings.

To maintain clinical equipoise and ensure the feasibility of this randomized controlled trial, we have chosen to focus on patients with shorter durations of persistent AF. These patients are hypothesized to have a lower likelihood of requiring EIVOM or other advanced substrate modification strategies. This

inclusion criterion allows us to evaluate the efficacy and safety of catheter ablation performed in non-fluoroscopic electrophysiology (EP) labs while minimizing the potential confounding effects of more complex ablation requirements. This approach ensures a balanced assessment of outcomes and aligns with the study's goal of evaluating PVI as the primary ablation strategy in a fluoroscopy-free context.

4 Data Collection

An Electronic Data Capture (EDC) system will be employed for the collection and secure storage of study data. The system is equipped with several built-in data integrity features, including range checks, logic checks, and mandatory data field requirements to ensure the accuracy and completeness of entries. Each investigator will be granted a unique, password-protected login to access the database, and any alterations to subject data will be logged to maintain a clear audit trail.

Primary data will be sourced from medical charts and procedural records, complemented by information gathered during structured interviews to assess quality of life (QoL) and other study-related metrics. Data collection will be managed by independent personnel who are not involved in the clinical care or procedural treatment of study subjects. Baseline, pre-procedural, and post-procedural data will be extracted from the medical record, standard questionnaires, physical examinations, and laboratory tests conducted during office visits. Physicians performing the ablation procedures will be responsible for accurate and timely documentation of relevant procedural data in the medical record.

Follow-up assessments will occur at the 1-, 2-, 3-, 6-, 9-, 12-month mark and may be conducted through in-person interviews. However, in-person interviews are strongly recommended to ensure the most comprehensive evaluation. During these visits, subjects will complete standardized questionnaires, undergo physical examinations, and have laboratory tests performed as needed. A trained study coordinator will conduct the interviews, following a standardized protocol to ensure consistency across all sites.

